The benefits of a HFib diet are supported extensively in the literature. Fiber protects against increasing body weight³⁰⁻³³, promotes fat loss³⁴⁻³⁹, increases satiety⁴⁰, and improves the metabolic and inflammatory profiles^{30,41-47}. Evidence that a HFib diet can reduce body weight and fat mass independent of a reduction in energy intake was highlighted in a recent meta-analysis⁴⁸ and a RCT in adults with MetS^{49,50}. The effect is hypothesized in part to be mediated through the powerful prebiotic effect of fiber that favorably shifts the gut microbiota leading to reduced weight gain⁴⁸, inflammation⁵¹, improved metabolic profile⁵¹, and prevention of fat accrual^{34-37,51}. Our working hypothesis is that consuming a HFib diet (≥ 30 g/day) will reduce GWG and fat accretion by diluting energy density, reducing hunger thereby reducing energy intake, and changing the gut bacteria composition. Our pilot data (n=20) found a 12 wk HFib pregnancy intervention reduced Firmicutes and increased Bacteroidetes, which was associated with reduced weight gain and fat accretion⁵². Current fiber intake of pregnant women is 17.3 g/day⁵³, well below the recommended intake (28 g/day⁵⁴), and triggering fiber to be classified as a nutrient of concern⁵⁵. Thus, increasing fiber intake has high potential for impact. However, RCTs in pregnant women are lacking to understand if this is an effective intervention strategy.

The project objective is to block randomize n=56 pregnant women to either a HFib diet or usual care. Eighteen weekly lessons will educate women on eating a HFib diet. To ensure fiber intake is met, daily snacks (10-12 g/day) will be provided. Weight gain, fat accretion, and stool microbiota will be measured twice during pregnancy (pre- and post-intervention) and assessed at 2 months, 6 months, and 12 months postpartum. Infant body composition will be measured at 2 weeks, 2 months, 6 months, and 12 months. The aims are:

Primary Aim 1: Assess the between group difference in maternal weight gain and fat accretion. H1: The HFib group will gain less weight and accrue less fat mass when compared to the control group.

Primary Aim 2: Compare fiber intake and dietary quality between groups. H2: The HFib group will consume more fiber and have a higher diet quality during pregnancy and postpartum.

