Secondary Aim 1: Characterize between group differences in the gut microbiome composition and diversity (alpha and beta). H1: The HFib group will have a greater change in gut microbiota composition, taxonomy, and diversity that will be detected during pregnancy and postpartum.

Secondary Aim 2: Determine if there are between group differences in early infant fat accrual. H2: Offspring born to women in the HFib group will have lower fat accrual.

Secondary Aim 3: Determine if there are differences in markers of metabolic, inflammatory, and brain health during pregnancy and postpartum. H3: The HFib group will be characterized by more favorable levels of metabolic, inflammatory, and brain health markers at all time points measured.

Impact: Prior intervention design has not addressed the MetS state of normal pregnancy. Dietary fiber counteracts the components of the MetS. Increasing fiber intake may positively impact the drivers of poor maternal outcomes that prior studies failed to show. Our study has potential to succeed where others have failed because we designed treatment to target the metabolic shifts that occur during normal pregnancy. This proposal is innovative because we are measuring the intervention impact on fat accrual and the microbiota in mother and early offspring fat accrual. This proposal would fill a large research gap.

RESEARCH STRATEGY

A) SIGNIFICANCE

A1) Why maternal excessive weight gain is an important problem: Overall, 55% of women gain excessive gestational weight^{3,4} though disparities exist within BMI groups; 62% of women with a high normal BMI (22-24.9 kg/m²) and ~70% of overweight and obese women gain excessively^{3,4}. Maternal overweight and excessive gestational weight gain (GWG) are associated with poor offspring outcomes including increased infant fat mass (FM)^{3,56} and increased FM in childhood^{57,58} and adulthood⁵⁹. Research shows a strong relationship between maternal excessive GWG and offspring obesity development^{60,61}, diabetes, and cardiovascular disease^{62,63}. Maternal conditions related to excessive GWG include hypertension^{64,65} and gestational diabetes (GDM)^{66,67}. Many women develop overweight or obesity during the childbearing years⁶⁸. Women who gain excessively are more likely to retain 10 to 20 lbs at 12 months postpartum⁶⁹. Effective interventions to prevent excessive GWG are desperately needed.

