C7c) Satisfaction survey: Satisfaction will be measured with three questions measured on a 5-point Likert scale at the completion of the study: "How confident are you that you will stick to the study diet?"; "I am always hungry on this diet"; and "This diet is a benefit to my health". Responses for the confidence question will be: not at all, not very, somewhat, very and extremely confident. Responses for the hunger and benefit to health questions will be: strongly agree, agree, neutral, disagree and strongly disagree.

C7d) 24-hour dietary recall: Three multiple-pass 24-hour dietary recalls (2 weekday and 1 weekend day) will be collected by trained research staff at baseline, end of intervention, and 2, 6, and 12 months postpartum to characterize energy and nutrient intake (1 in person, 2 via phone per each visit using a standardized food amounts booklet). One 24-hour recall will be obtained every four weeks during the intervention to assess fiber goal adherence. Multiple-pass 24-hour recalls accurately estimate dietary intake^{110,111} and contain less reporting bias than diet records^{110,112}. One 24-hour dietary recall will be administered to the child's caregiver at 2 weeks, 2 months, 6 months, and 12 months to characterize the diet of the child. The recalls will be entered into the Nutrition Data System for Research (NDS-R, version 2020, Minneapolis, MN) for macro- and micronutrient analysis.

C7e) Fecal Sample Collection: Stool will be collected five times throughout the study (baseline, end intervention, and 2, 6 and 12 months postpartum) from the mother and four times throughout the study from the infant (2 weeks, 2 months, 6 months, and 12 months). OMNIgene GUT and OMNImet GUT stool collection kits (DNAGenotek, Canada) will be shipped to women with specific instructions on collection and storage at home. Women will bring collected samples to their study visit. DNA extraction will be completed at KUMC under the supervision of [name]. Library preparation and microbial profiling using 16S V4 sequencing will be completed at KU Lawrence.

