C7k) Maternal blood draw: Maternal venous blood will be collected at 5 times through the study (baseline, end of intervention, 2 months, 6 months, and 12 months postpartum) after an overnight fast by a trained phlebotomist. A total of two 4-mL EDTA (lavender top) tubes (1 will be filled ½ full), one 10-mL EDTA, one 7.5-mL serum (tiger top) tube, and one 8.5mL serum tubes will be collected. At the baseline visit and additional one 6-mL ACD (yellow top) plasma vacutainer will be collected for ApoE genotyping. All tubes will be placed on ice and processed within 24 hours, including aliquoting for analysis. All tubes will be appropriately labeled with the study identification number, date (mm/dd/yyyy), and time (24-hour time, hh:mm). Blood samples will be analyzed to assess biomarkers related to cardiometabolic health (including serum lipids, glucose metabolism, and inflammation), gut metabolites (short chain fatty acids) and neuronal health (including assessment of underlying ApoE genetics). Samples will be sent to Quest Diagnostics for cardiometabolic markers (standard lipid panel (total cholesterol, triglycerides, HDL-C, LDL-C (calculated), Cholesterol/HDL ratio (calculated), and non-HDL-C (calculated)), hemoglobin A1C, plasma glucose, serum insulin, and high sensitivity- C-reactive protein). All other samples will be stored at -80°C for analysis. Batched samples will be analyzed at KUMC according to the protocols of the manufacturer using the following formats:, SIMOA (neurofilament-light and inflammatory cytokines), and polymerase chain reaction (ApoE genotype). Unused samples will be banked for future evaluations related to nutrition and brain health including free cell RNA analysis at KUMC.

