C7t) Breastmilk analysis: Participants who choose to breast feed will be asked to pump one breast until empty, homogenize the breastmilk by stirring, and return 20-mL to the study team for nutrient analysis. Participants will be asked to do this at 1 month, 2 months, 3 months, 4 months, 5 months, and 6 months, freeze it, and return it to the study team at the 2-month and 6-month visits. The remainder of the breastmilk collected can be kept by the participant and fed to their infant. Any leftover sample after initial nutrient analysis will be banked for future evaluations related to nutrition and brain health and KUMC.

C8) Steps to maximize adherence and retention: We will be using incentives for study visits, incentives for reporting goals, and regular short-term performance and feedback.

C8a) Incentive system: Participants will be compensated \$100 for each of the 6 study visits: baseline, end intervention, 2 weeks postpartum, 2 months postpartum, 6 months postpartum, and 12 months postpartum totaling up to \$600 for completion of all visits. Participants asked to return for repeat infant DXA (no more than 2 at each study timepoint) will be compensated an additional \$50. Compensation will be provided on a ClinCard, which is given at enrollment. After each visit study staff will load their unique card number with the respective pay. Participants can use the card anywhere Mastercard is accepted, and study staff does not have access to where the money will be spent.

C8c) Monitoring retention: When participants miss a session or reporting of behaviors, they will be contacted and a standardized protocol according to attendance and adherence demands will be used to make every effort to retain the participant or encourage reporting. This will be documented and used for program evaluation.

C9) Statistical analysis: The purpose of this study is to attain feasibility data therefore the small sample size does not afford the power to detect significance but to identify promising trends and relationships.

Analysis for Aim 1 H1: A t-test will be used to determine if there is a difference in maternal weight gain and fat accretion between the two groups.

Analysis for Aim 2 H2: A t-test will be used to quantify if there is a difference in fiber intake and dietary quality between the two groups.

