Analysis for secondary Aim 1 H1: Repeated measures ANCOVA will be used to assess the difference in gut microbiome composition and diversity from baseline to study end between groups.

Analysis for secondary Aim 2 H2: A t-test will be used to determine if there is a difference in infant fat accrual between groups.

Analysis for secondary Aim 3 H3: A t-test will be used to determine if there is a difference in metabolic, inflammatory, and brain health markers.

Process evaluation: A process evaluation will be completed.

C10) Study challenges: A primary study challenge is the recruitment and retention. [name] has completed protocols successfully recruiting participants from the OB clinics at KUMC. [name], KUMC head of OBGYN, reports 1800 annual deliveries take place at KUMC with ~40% overweight. A second challenge is to assure the fidelity of the interventions. [name] will listen to 20% of GBPC sessions and compare the content delivered to a standardized checklist. If less than 80% of content is covered, [name] will re-train the Dietitian. A third challenge is to ensure subjects are attending sessions and reporting behaviors. We had a high degree of weekly reporting in our pilot study and anticipate a similar response rate in this pilot.

C11) Expected results: We anticipate the Hfib intervention will successfully prevent excessive GWG. The Hfib intervention holds promise to be delivered in routine clinical care. If the results are positive, the next study would be to adapt and embed the Hfib intervention in routine clinical care. The literature supports preventing excessive GWG has a high likelihood to greatly improve the health of both mothers and their offspring however there is variable success in published interventions. This supports the need to design and test interventions informed by prior study failures.

C12) Environment: The environment at KUMC is well suited to conduct this research.

References:

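### C9 plans bare t-tests for Aim 2 and secondary Aim 3 although these outcomes are measured at baseline; baseline-adjusted ANCOVA is expected to narrow the intervals once the baseline/follow-up correlation exceeds about 0.14

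*Combined protocol and SAP*

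**What the plan says.** Section C9 gives each aim one sentence. For primary Aim 2: "A t-test will be used to quantify if there is a difference in fiber intake and dietary quality between the two groups". For secondary Aim 3: "A t-test will be used to determine if there is a difference in metabolic, inflammatory, and brain health markers". Neither sentence states a covariate, a visit, or whether the follow-up value or the change from baseline is tested.

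The same section treats the microbiome differently: "Repeated measures ANCOVA will be used to assess the difference in gut microbiome composition and diversity from baseline to study end between groups".

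The hypotheses in the Specific Aims are broader than one visit. H2 reads "The HFib group will consume more fiber and have a higher diet quality during pregnancy and postpartum", and H3 reads "The HFib group will be characterized by more favorable levels of metabolic, inflammatory, and brain health markers at all time points measured".

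The baseline data exist. Under C7d, three dietary recalls are "collected by trained research staff at baseline, end of intervention, and 2, 6, and 12 months postpartum". C7k (fasting blood) and C7o (cognitive testing) use the same five occasions. ApoE genotype is the exception: its tube is drawn only at baseline.

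C9 also states the trial's limits: "The purpose of this study is to attain feasibility data therefore the small sample size does not afford the power to detect significance". It presents the study as a search for promising trends.

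**The concern.** A two-sample t-test on follow-up values discards the baseline measurement. A t-test on changes uses it with a fixed weight of one, which adds noise when the correlation is modest. ANCOVA estimates the weight and normally does at least as well as either. A trial that disclaims power has effect estimates with intervals as its useful output, so precision is what matters.

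Chance imbalance is also a live issue with about 28 women per arm, because an unadjusted follow-up comparison carries part of any baseline difference into the result.

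Finally, the wording leaves much to be chosen after the data are seen. C7k lists ten commercial-laboratory results. With four follow-up visits and two readings (follow-up or change), that allows 10 × 4 × 2 = 80 different t-tests. For fiber and diet quality, counting diet quality as one score, the figure is 2 × 4 × 2 = 16.

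The point is limited to outcomes measured at both baseline and follow-up. Aim 1 is outside it: C7a already defines weight gain as a change from measured baseline weight. If body weight has a high correlation (0.9 assumed), ANCOVA gains little over a change score (SE ratio 0.98).

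**Working it through.** C9 offers no power calculation to reproduce.

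**Inputs.** N = 56 (Specific Aims). The allocation ratio is not stated, so 28 per arm is assumed. The baseline/follow-up correlation ρ and all SDs are absent from the documents, so a range of ρ is shown in SD units. Women are taken as independent, with equal variances and all 56 analysed, unless stated otherwise.

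**Versus a t-test on follow-up values.** Charging the lost degree of freedom and expected baseline imbalance:

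variance ratio = (1 − ρ²) × k, with k = 1 + 1/(N − 4) = 1 + 1/52 = 1.0192.

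The 95% half-width is t × √(2/28), with 54 df unadjusted (0.536 SD). The adjusted half-width uses 53 df and is multiplied by the SE ratio.

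| ρ (assumed) | Variance ratio | SE ratio | Equivalent N (56 / ratio) | Half-width, SD |
|---|---|---|---|---|
| 0 | 1.0192 | 1.010 | 54.9 | 0.541 |
| 0.2 | 0.9785 | 0.989 | 57.2 | 0.530 |
| 0.3 | 0.9275 | 0.963 | 60.4 | 0.516 |
| 0.5 | 0.7644 | 0.874 | 73.3 | 0.469 |
| 0.6 | 0.6523 | 0.808 | 85.8 | 0.433 |

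Break-even: ρ = √(1 − 1/k) = 0.137 for the SE and 0.140 for interval width. For expected width it rises to 0.148, 0.157 and 0.168 with 50, 45 and 40 women analysed.

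These are expectations. In 40,000 simulated trials the ANCOVA interval was the narrower one in about 56% of trials at ρ = 0.2, 80% at 0.3 and 99% at 0.5.

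**Versus a t-test on changes.** The change has variance 2(1 − ρ), so the SE ratio is √(k(1 + ρ)/2) = 0.782, 0.814, 0.874, 0.931 and 0.984 at ρ = 0.2, 0.3, 0.5, 0.7 and 0.9. Break-even is 2/k − 1 = 0.962, with no lower threshold.

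**Chance imbalance.** One standard error of the baseline difference is √(2/28) = 0.267 SD. It shifts a follow-up comparison by ρ × 0.267 = 0.053, 0.080, 0.134 and 0.160 SD at ρ = 0.2, 0.3, 0.5 and 0.6.

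**Fiber.** C2 excludes women at 25 g/day or more, which restricts the baseline range. A normal distribution truncated at 25 was used, treating the screening value as baseline. The two cases were mean 15 g (C5c) with SD 5, and mean 17.3 g (Specific Aims) with SD 8; both SDs are assumed. The baseline variance falls to 0.886 and 0.619 of its unrestricted value.

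- An unrestricted ρ of 0.5 becomes 0.478 and 0.413: SE down 11.3% and 8.1%.
- An unrestricted ρ of 0.3 becomes 0.284 and 0.240: SE down 3.2% and 2.0%.

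If the 10–12 g/day from snacks adds fully to intake, the contrast is 10/8 = 1.25 to 12/5 = 2.4 SD, and t-test power is at least 99.6%. At half that contrast (5–6 g) power is 63–99%.

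**Clustering.** With an assumed ICC of 0.05 and groups of 8 in one arm, the design effect there is 1 + 7 × 0.05 = 1.35. The SE rises by √((1 + 1.35)/2) = 1.084 and the half-width to 0.581 SD. In 12,000 simulated trials (four intervention groups of 7, ICC 0.05) the ANCOVA/t-test SE ratio was 0.990, 0.968, 0.890 and 0.832 at ρ = 0.2, 0.3, 0.5 and 0.6.

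**Baseline taken after assignment is known.** Suppose knowledge of assignment shifts baseline by 0.2 SD in one arm, with ρ = 0.5 and a true effect of 0.6 SD. Simulated estimates were 0.598 (follow-up), 0.498 (ANCOVA) and 0.398 (change), so the biases are about 0, 0.10 and 0.20 SD.

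**The case against.** The strongest reply is that this is efficiency only. The t-test is unbiased, the study calls itself a feasibility study, and no success rule depends on interval width. The gain also rests on a correlation that the documents do not give. There are reasons to expect a low one: baseline falls anywhere in 12–20 weeks, metabolism shifts during pregnancy, and follow-up runs to 12 months postpartum. At ρ of 0.2–0.3 the saving is 1–4%. All of that stands, and it limits the severity. It does not remove the point, because the cost at ρ = 0 is about 1%.

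Fiber is the weakest case. Power is already high at full contrast. The intervention also pushes women toward a common goal, which may flatten the baseline slope in that arm. With assumed correlations of 0.5 in control and 0 in the intervention arm the SE ratio is 0.98; with 0.3 and 0 it is 1.00. So the gain can vanish for fiber, but no harm follows.

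The hypotheses do give time frames, and H3 speaks of levels, which favours follow-up values. They still select no visit or model. Naming end of intervention as the main visit is a choice, and the later visits should remain as contrasts.

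Clustering by intervention group can cost more than the adjustment gains, and ANCOVA does not model it. Skewed markers and dropout matter too; the earlier pilot lost 3 of 12 usual-care women. Clustering and skewness affect the planned t-test equally. A missing baseline value is a cost specific to ANCOVA and needs a stated rule.

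**Conclusion.** The concern holds, as a gap in precision and pre-specification and not as a source of bias. For ρ between about 0.14 and 0.96, ANCOVA is expected to give a narrower interval than either reading of C9. Below 0.14 it loses at most about 1% in SE to a follow-up t-test. The benefit ranges from negligible (1% at ρ = 0.2) to material (13% at 0.5, equivalent to about 73 women instead of 56).

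These figures assume 28 independent women per arm, all analysed, and an undocumented ρ. The relative gain largely survives an ICC of 0.05, although absolute intervals widen. The change matters more for diet quality and the Aim 3 markers, for which no effect size is given, than for fiber. It should be made; confidence is medium because the size depends on ρ.

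**What to change.** In C9, for every Aim 2 and secondary Aim 3 outcome measured at both baseline and follow-up (not ApoE genotype), replace the t-test with a regression of the follow-up value on arm and that outcome's own baseline value. Name end of intervention as the main visit. Treat 2, 6 and 12 months postpartum as further contrasts, by separate ANCOVAs or one baseline-adjusted arm-by-visit mixed model. Report adjusted mean differences with 95% intervals. State how a missing baseline value is handled.

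Use as covariate only baseline values obtained before the woman learns her assignment. Item (2) of the human-subjects section mentions randomisation and baseline testing together without fixing their order, and this should be clarified. If the order cannot be shown for self-reported diet, keep the unadjusted follow-up comparison for that outcome, at the named visit. That fallback would leave Aim 2 unadjusted but would not affect the Aim 3 laboratory markers.

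The cost is SAP wording and one degree of freedom per outcome, with no new data. The postpartum contrasts add three estimates per outcome and should be labelled as such. Clustering by intervention group is not addressed by this change.

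### Secondary Aim 3 offers only a t-test for at least 13 markers over four post-baseline visits, with no lead visit, longitudinal model or rule for calling a trend promising

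*Combined protocol and SAP*

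**What the plan says.** The whole analysis for Secondary Aim 3, in C9, is one sentence: "A t-test will be used to determine if there is a difference in metabolic, inflammatory, and brain health markers". It does not say whether levels or changes are compared, at which visit, or with what adjustment. The hypothesis in the Specific Aims is wider: "The HFib group will be characterized by more favorable levels of metabolic, inflammatory, and brain health markers at all time points measured".

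No list of Aim 3 markers is given. C7k (maternal blood draw) names these:
- a "standard lipid panel (total cholesterol, triglycerides, HDL-C, LDL-C (calculated), Cholesterol/HDL ratio (calculated), and non-HDL-C (calculated" set, which is six lipid results
- "hemoglobin A1C, plasma glucose, serum insulin, and high sensitivity- C-reactive protein", which is four more
- "SIMOA (neurofilament-light and inflammatory cytokines", which is neurofilament-light and an unstated number of cytokines

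C7o separately describes a cognitive battery covering five domains. C7k and C7o both schedule baseline, end of intervention, and 2, 6 and 12 months postpartum.

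C9 opens by limiting its own ambition: the study is for feasibility, and "the small sample size does not afford the power to detect significance but to identify promising trends and relationships". No significance level, multiplicity rule or meaning of a promising trend is stated anywhere. For Secondary Aim 1, by contrast, C9 names a repeated-measures ANCOVA.

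**The concern.** A two-sample t-test handles one marker at one time. A hypothesis about many markers at all visits, paired with a t-test, most naturally leads the analyst to test each marker at each visit. C9 gives no way to tell a real signal from the best of many chance results. It also leaves open which visit will be presented as the result once the data are seen.

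Sorting signals is the study's declared purpose ("to identify promising trends and relationships"). Markers picked out here could be carried into later work. The stake is therefore wasted effort on false leads and a reporting choice that was not fixed in advance. The trial's primary comparisons are not affected.

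**Working it through.** The plan states no error rate or power for this aim, so there is no figure of its own to reproduce.

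**Inputs from the documents**
- Blood measures (C7k): 6 lipids + 4 other laboratory results + neurofilament-light + at least 2 cytokines (the word is plural) = 13. Short chain fatty acids are mentioned without a number and are not counted.
- With the five cognitive domains (C7o): 13 + 5 = 18.
- Visits: 5 scheduled, less baseline = 4.
- Sample size: 56 women.

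**Assumptions, because the plan is silent**
- Two-sided 0.05 per test.
- 28 women per arm with no dropout.
- Correlation between markers 0 to 0.5 and between visits 0 to 0.8.

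**Step 1. Expected false positives if every marker is tested at every visit.** Tests × 0.05, whatever the correlation:
- 13 × 4 = 52 tests; 52 × 0.05 = 2.6
- 18 × 4 = 72 tests; 72 × 0.05 = 3.6

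**Step 2. Chance of at least one, if tests are independent.** 1 − 0.95^k:
- k = 52: 0.931
- k = 72: 0.975

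**Step 3. Chance of at least one, with correlation.** Null simulation, pooled t-tests, 2,500 to 3,000 runs per setting. The larger set was run with 17 markers (one cytokine counted). This matters little: independent tests give 0.969 for 17 markers and 0.975 for 18.

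| Marker r, visit r | 13 markers × 4 | 17 markers × 4 |
|---|---|---|
| 0, 0 | 0.93 | 0.97 |
| 0.2, 0.5 | 0.86 | 0.92 |
| 0.3, 0.7 | 0.78 | 0.85 |
| 0.5, 0.8 | 0.63 | 0.68 |

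The three calculated lipids were then computed from the measured ones, using assumed means and SDs. Over marker r 0 to 0.3 and visit r 0.5 to 0.8 the ranges are 0.68 to 0.84 (13 markers) and 0.78 to 0.92 (17 markers). Hence roughly 70 to 97%, with the heaviest correlation tried falling somewhat below.

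**Step 4. Other readings of the same sentence**
- One visit only, independent: 10 measured markers 1 − 0.95^10 = 0.40; 13 markers 1 − 0.95^13 = 0.49; 18 markers 1 − 0.95^18 = 0.60. Simulated for 17 markers with calculated lipids: 0.47 to 0.54.
- Favorable direction only (0.025), 17 markers × 4 visits: 0.82 if independent, about 0.46 to 0.75 with marker r 0 to 0.3 and visit r 0.5 to 0.8.
- Same marker significant in the same direction at all four visits: about 0.02 (visit r 0.5) to 0.16 (visit r 0.8).

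**Step 5. Effect of naming one lead visit.** 13 contrasts × 0.05 = 0.65 expected false leads. With the three calculated lipids set aside, 10 × 0.05 = 0.5. The comparable figure in Step 1 is 2.6.

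**Step 6. What a strict false-discovery gate would cost.** Take 28 per arm, one visit, 14 markers correlated 0.25 and one true effect of 0.5 SD (all assumed). Detection of that effect is about 45% at p < 0.05 and about 19% at a Benjamini-Hochberg q of 0.10 or less.

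**The case against.** The strongest reply is that C9 already disclaims power for significance and calls the study a feasibility exercise. Aim 3 is secondary, and C11 ties the next study to the weight-gain result. On that view formal error control for an exploratory screen is a matter of preference. Much of this stands: strict familywise control is not required, and Step 6 shows that a hard false-discovery threshold would more than halve the chance of keeping a real moderate effect. It does not excuse leaving the lead visit, the model and the meaning of a promising trend open.

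A reader might also infer that the plan tests 17 or more markers separately at four visits, so that a false lead is almost certain. The documents do not support that, for four reasons:
- They never assign the cognitive domains to Aim 3. The supported floor is 13 blood measures.
- They do not say that visits are tested separately. That is inferred from pairing a t-test with a hypothesis covering all visits.
- A figure of 97% needs independent tests, yet three lipids are calculated from others and the same women are measured repeatedly.
- The hypothesis is directional and speaks of all time points. If read as requiring consistency over visits, false leads would be uncommon (0.02 to 0.16), though no such decision rule is written.

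**Conclusion.** The gap is real and modest. At least 13 blood measures at four post-baseline visits are covered by a single t-test sentence, with nothing to say which result leads. Under marker-by-visit testing, the expected number of false positives with no fiber effect is about 2.6 to 3.6, and at least one is likely but not certain. Under one-visit testing it is close to an even chance.

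All of these rates rest on the assumed 0.05 level. The probabilities also rest on the assumed correlations, and the simulated ones on 28 per arm without dropout. The spread across readings, from about 0.02 to 0.97, is itself the reason to fix the reading before analysis. This is an inexpensive improvement to a secondary aim and does not threaten the trial.

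**What to change.** In C9, replace the t-test sentence for Secondary Aim 3 with the following:
- List the markers, and say whether the cognitive domains are among them.
- Fit one longitudinal model per marker over the post-baseline visits, adjusted for the baseline value already collected. This is in line with the repeated-measures approach that C9 takes for Secondary Aim 1.
- Make the arm difference at end of intervention the single lead result for each marker. Report the later visits from the same model as supportive.
- Treat the three calculated lipids as descriptive.
- Report every estimate with a 95% CI. Show Benjamini-Hochberg q-values across the end-of-intervention contrasts alongside, as a guide and not as a condition for calling a lead.

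The drop in expected false leads comes from naming one lead visit. The model's part is to use the repeated measurements and the baseline together.

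The cost is SAP wording and slightly more programming, with no extra women, visits or samples. The downside is that a difference seen at one postpartum visit alone would no longer be highlighted on its own.
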